#### 5.3.1.3. Analysis Methods

The number and percentage of subjects who achieve a response will be summarized at each time point during the double-blind phase by treatment group. The point estimate and 2-sided 90% confidence interval will be provided for the relative response using a Mantel-Haenszel test controlling for region and baseline insomnia status (present/absent).

The cumulative response rate, defined as the percentage of subjects experiencing at least a given value of percent reduction from baseline to the end of Week 6 in MADRS total score, will be presented graphically, for both observed and LOCF data.

The cumulative distribution function of the time to sustained response will be estimated by the Kaplan-Meier method. Time to sustained response will be summarized (number of sustained responders, number of censored subjects, median, 25th and 75th percentile, if estimable) by treatment group. Sustained response is defined as the first occurrence of response on Day 8 or Day 22 that is maintained through the end of Week 6 assessment. Subjects are allowed one excursion (non-response) on a subsequent visit prior to Day 42, however the score must show at least 25% improvement. Subjects who discontinue early are not considered to have sustained response. A stratified log rank test (stratified for region and baseline insomnia status) will be used to test the hypothesis that there is no difference between the JNJ-42847922 dose groups and placebo in the probability of achieving sustained response.

A variation of definition for sustained response will be explored, for which no excursion is allowed. The analyses mentioned above will be repeated for this variation.

#### 5.3.2. Remission of Depressive Symptoms

#### 5.3.2.1. Definition

A secondary efficacy endpoint is the proportion of subjects with remission of depressive symptoms at the end of Week 6, defined as a MADRS total score  $\leq 8$ ,  $\leq 10$ , or  $\leq 12$  at the end of Week 6. Subjects who do not meet such criterion will be considered as non-remitters. Observed case analysis, i.e., no imputation for subjects with missing values, will be explored. The calculation of the MADRS total score is described in Section 5.2.1.

#### 5.3.2.2. Analysis Methods

The number and percentage of subjects who achieve remission (based on each of the 3 definitions) will be summarized at each time point during the double-blind phase by treatment group.

The point estimate and 2-sided 90% confidence interval will be provided for the relative risk of remission using a Mantel-Haenszel test controlling for region and baseline insomnia status (present/absent).

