#### 1.4. Sample Size Justification

The calculation of the sample size is based on the primary efficacy endpoint (change from baseline to the end of Week 6 for the MADRS total score). The assumptions for the effect size were based on published literature and the clinically meaningful difference between groups to be detected.

The total sample size is calculated on the basis of the generalized Multiple Comparison Procedure-Modeling (MCP-Mod) test applied to the placebo and the JNJ-42847922 dose groups at the final analysis. Approximately 280 randomized subjects will provide an average weighted power of approximately 85% depending on the underlying true dose-response shape, assuming a 1-sided significance level of 0.05, a treatment difference from placebo of 4.5 points in change in MADRS total score, a standard deviation of 10, and a 25% overall dropout rate.

The data cutoff for the interim analysis will be 6 weeks after randomization of 160 subjects, which corresponds to approximately 57% of the sample size of the study. This number of subjects provides approximately 93% power to detect a dose-response relationship, depending on

the underlying true dose-response shape, assuming a treatment difference of 4.5, and a standard deviation of 10 when tested by means of the MCP-Mod approach at the 30% significance level (1-sided).

Further details regarding the interim analysis will be specified in a separate charter and interim analysis SAP.

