#### 1.5. Randomization and Blinding

Central randomization will be implemented in this study. Subjects will be randomly assigned based on a computer-generated randomization schedule prepared before the study by or under the supervision of the sponsor.

At the start of study enrollment, subjects will be randomly assigned to receive 1 of 3 treatments in a 2:1:1 ratio to placebo:JNJ-42847922 20 mg:JNJ-42847922 40 mg.

After the interim analysis, subjects will be randomly assigned to study drug, with the allocation ratio adapted according to the dose-response curve observed at the time of the interim analysis. Subjects will be assigned to receive placebo or one of the JNJ-42847922 doses (potential doses include 10 mg, 20 mg, 40 mg).

The randomization will be balanced by using randomly permuted blocks and will be stratified by region (United States [US], Europe, and Japan) and by insomnia status (significant insomnia symptoms [ISI score  $\geq$ 15] at baseline versus no significant insomnia symptoms [ISI score <15] at baseline). In order to randomize approximately equal proportions of subjects with and without significant insomnia symptoms at baseline, the number randomized in either stratum will be capped at 60% of the planned total sample size.

The interactive web response system (IWRS) will assign a unique treatment code, which will dictate the treatment assignment and matching study drug kit for the subject. The requestor must use his or her own user identification and personal identification number when contacting the IWRS, and will then give the relevant subject details to uniquely identify the subject.

To maintain the study blind, the study drug container will have a label containing the study name, study drug number, and reference number. The label will not identify the study drug in the container. However, if it is necessary for a subject's safety, the study blind may be broken and the identity of the study drug ascertained. The study drugs will be identical in appearance and will be packaged in identical containers.

In general, randomization codes will be disclosed fully only when the study is completed and the clinical database is closed. However, for the interim analysis, the randomization codes and the translation of randomization codes into treatment and control groups will be disclosed to those authorized and only for those subjects included in the interim analysis.

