## 5.2.3.1. MCP-Mod Analysis

The primary efficacy endpoint will be evaluated using the generalized MCP-Mod approach. The MCP-Mod approach provides a method for dose-finding using model-based estimation rather than hypothesis testing via pairwise comparisons. The analysis will be done in two steps.

First, a mixed model for repeated measures (MMRM) analysis of the observed data from the placebo and JNJ-42847922 groups will be used as the method of addressing missing data and to

adjust for important covariates. The MMRM will include region (as defined in Section 2.6), time (scheduled Week), treatment (placebo and JNJ-42847922 dose groups), baseline insomnia status (present/absent), and treatment-by-time interaction as factors and baseline MADRS total score as a covariate. An unstructured variance-covariance matrix will be used for observations clustered by subject. In case of convergence problems, alternative variance-covariance structures will be tried in the following order, with the first structure that converges being used in the analysis: heterogeneous Toeplitz, standard Toeplitz, and AR(1) with separate subject random effect. Subjects in the full analysis set who do not have complete data will still contribute to the estimates at the end of Week 6, but will have less weight in the analysis than those subjects with complete data. The Kenward-Roger method will be used for approximating the denominator degrees of freedom. Based on the MMRM, the least-squares (LS) mean estimates for each JNJ-42847922 dose group and placebo at Week 6 and the corresponding variances will be obtained.

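### Remission depends on the starting MADRS score, but SAP 5.3.2.2 compares arms without baseline MADRS: a valid estimate that gives up a little precision

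*SAP*

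**What the plan says.** SAP 5.3.2.1 defines remission as an absolute MADRS total at Week 6, with three cut-offs: 8, 10 and 12 or less. SAP 5.3.2.2 gives a point estimate and two-sided 90% CI for the "relative risk of remission using a Mantel-Haenszel test controlling for region and baseline insomnia status". Response (SAP 5.3.1.3) is handled in the same way, as "relative response using a Mantel-Haenszel test controlling for region and baseline insomnia status", but it is a percentage change from the subject's own baseline.

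The primary MMRM in SAP 5.2.3.1 has "treatment-by-time interaction as factors and baseline MADRS total score as a covariate". The LOCF ANCOVA in SAP 5.2.3.3 also adjusts for baseline MADRS. Randomisation is stratified by region and insomnia status, not by baseline MADRS (Protocol 5; SAP 1.5). SAP 5.1.2 reports remission twice: on observed cases, and with missing subjects counted as non-remitters. Neither document plans a remission comparison adjusted for baseline MADRS.

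**The concern.** A fixed cut-off asks more of a sicker subject. Under Inclusion Criterion 5 the lowest possible baseline is 25 x 0.80 = 20. From 20, a score of 12 needs a fall of 8 points (40%); from 40 it needs 28 points (70%). Baseline is therefore prognostic for remission almost by construction, and it is the one obvious predictor missing from the comparison.

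Two things follow. The remission ratio is less precise than it could be with data already in hand. And if one arm happens to start sicker, its remission rate is pulled down with no correction, while the primary MADRS comparison beside it is corrected. The two can then drift apart for a reason unrelated to treatment, in a study meant to guide the choice of Phase 3 doses and endpoints.

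**Working it through.** **The plan's own figure.** The only power statement concerns the primary endpoint: "Approximately 280 randomized subjects will provide an average weighted power of approximately 85"%, "assuming a 1-sided significance level of 0.05", with "a treatment difference from placebo of 4.5 points in change in MADRS total score", "a standard deviation of 10, and a 25% overall dropout rate". With 280 x 0.75 = 210 evaluable subjects, a "2:1:1 ratio to placebo:JNJ-42847922 20 mg:JNJ-42847922 40 mg" and the SAP's three candidate shapes, the maximum-contrast test has power 84.0% (linear), 92.5% (Emax) and 81.7% (exponential). The mean is 86.1%, so the figure reproduces. This point does not touch it. No power or rate is stated for remission.

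**Assumed inputs** (none is in the documents except the floor and the dropout rate):
- baseline B normal with mean 32 and SD 4.5, cut off below 20;
- residual SD 10;
- mean change m from -10 to -14.5;
- slope s of change on baseline from -0.2 to -0.4;
- dropout 25%, independent of baseline.

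**Formulas.**
- Week 6 score: Y = B + m + s(B - 32) + e.
- Remission at cut-off c: P(Y <= c | B) = Phi((c - B - m - s(B - 32))/10), averaged over B to give the rate p.
- Slope of remission on baseline: k = cov(R, B)/var(B).
- Share of variance explained: r2 = cov(R, B)^2/[var(B) p(1 - p)].
- With dropouts counted as non-remitters, the rate becomes 0.75p, the slope 0.75k, and r2 is multiplied by 0.75(1 - p)/(1 - 0.75p).
- SE of a baseline difference, if 2:1:1 held for all 280 (140 versus 70): 4.5 x sqrt(1/140 + 1/70) = 0.66 points. The shift in the remission difference is k x 0.66.

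**Results** (range over the four combinations of m and s):

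| Cut-off | Rate | k per point | r2, complete | Shift, complete | r2, imputed | Shift, imputed |
|---|---|---|---|---|---|---|
| <=8 | 9-18% | 0.009-0.020 | 2.0-5.2% | 0.6-1.3 pp | 1.5-3.7% | 0.45-1.0 pp |
| <=10 | 12-24% | 0.012-0.023 | 2.5-5.8% | 0.8-1.5 pp | 1.8-4.0% | 0.6-1.1 pp |
| <=12 | 17-30% | 0.014-0.026 | 2.9-6.4% | 0.9-1.7 pp | 2.1-4.3% | 0.7-1.3 pp |

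Worked line, <=12 at the upper end: p = 0.301, r2 = 6.4%; imputed, 6.4% x 0.75 x 0.699/0.774 = 4.3%. Shift: 0.0262 x 0.66 = 1.7 points, and 0.75 x 1.7 = 1.3.

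In subjects, the gain is roughly r2/(1 - r2): 0.020/0.980 = 2% to 0.064/0.936 = 7% on complete data, and 0.015/0.985 = 1.5% to 0.043/0.957 = 4.5% with imputation.

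**Response, same assumptions.** r2 is 0.1-1.1%.

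**Second check by simulation** (105 versus 53 evaluable; baseline mean 33, SD 5; placebo change -13; effect 4.5). Adding continuous baseline MADRS to a logistic model raises one-sided 0.05 power for remission at <=12 from 66% to 68% when the slope of Week 6 score on baseline is 0.5, and from 57% to 61% at slopes of 0.8 and 1.0. For response it goes 71% to 71%, 69% to 68% and 69% to 69%. With no treatment effect, remission rejection rates are 5.2-5.6% without baseline and 5.5-5.8% with it (2,000 runs each). With baseline SDs of 4 and 6, adding a median split on baseline to the Mantel-Haenszel strata changes remission power by only -1 to +2 points. In that setting an active arm starting one point higher has its remission ratio lowered by about 5-10%.

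**The case against.** The planned analysis is not an error. Region and insomnia status are exactly the randomisation strata, and a Mantel-Haenszel ratio over them is a coherent, pre-specified choice. Baseline MADRS is tabulated by arm, so an imbalance would be seen. The endpoint is secondary, inference is nominal, and no dose decision is tied to it. All of this stands.

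Four stronger readings are tempting, and the documents do not support them.
- A reader might infer that the comparison is biased or its error rate inflated. It is not: arms randomised side by side are comparable, and the simulated error rates agree.
- A reader might infer that a promised covariate was dropped. Protocol 11.3 assigns the corresponding baseline to change-from-baseline endpoints and plans only frequency distributions for responders and remitters. The SAP goes further than the protocol here.
- A reader might extend the point to response. Its definition already contains the subject's own baseline, and adjustment gains essentially nothing.
- A reader might take the complete-data gain as the gain for the reported analysis. The SAP also counts missing subjects as non-remitters, which dilutes the link with baseline.

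Remission and the primary result can also differ for other reasons: non-remitter imputation and the primary estimand, which supposes that everyone stayed on treatment, answer different questions.

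**Conclusion.** The point holds for remission only, as a small and optional improvement. The planned estimate is valid. Leaving out baseline MADRS forgoes about 2-6% of explained variance on complete data and about 1.5-4.3% with dropouts counted as non-remitters. It also leaves a one-SE chance imbalance worth 0.6-1.7 percentage points (0.45-1.3 with imputation) uncorrected.

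These sizes rest on an assumed baseline distribution, slope and mean change, on dropout unrelated to baseline, and on 140 versus 70 subjects. Allocation may change at the interim, and a smaller, later-added 10 mg arm would have a larger chance imbalance. The primary result and the sample size are unaffected.

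**What to change.** In SAP 5.3.2.2, for each of the three cut-offs, add a logistic model with treatment, region, insomnia status and continuous baseline MADRS. Standardise it over the full analysis set to give the relative risk of each dose versus placebo, with a two-sided 90% CI by the delta method or bootstrap (name one). Keep the Mantel-Haenszel estimate as support, and as the stated fallback if the model does not converge. That could matter at <=8: the imputed rates implied above (0.75 x 9-18%, about 7-14%) give roughly 5-10 remitters in an arm of 70, and fewer in a smaller arm. Use baseline as a continuous term; a further Mantel-Haenszel stratum gains almost nothing and thins the cells.

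Leave SAP 5.3.1.3 (response) as it is. The cost is a short paragraph of specification and some code, with no new data. The downside is a little added complexity for a secondary endpoint.

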## 5.3.3. Shift in Insomnia Severity Index (ISI) Score Category

#### 5.3.3.1. Definition

A secondary efficacy endpoint is the shift in ISI score category from baseline to the end of Week 6. The calculation of the ISI score is described in Section 5.2.3.5. The scores are categorized as follows: score 0-7=no clinically significant insomnia; score 8-14=sub-threshold insomnia; score 15-21=moderate insomnia, and score 22-28=clinically severe insomnia.

## 5.3.3.2. Analysis Methods

The shift in ISI score category from baseline to the end of Week 6 will be presented. A frequency distribution of the ISI individual item scores at each time point will be provided by treatment group. In addition, descriptive statistics of the ISI score at Baseline and Week 6, as well as the change from baseline to Week 6, will be presented by treatment group. Descriptive statistics will also be provided for change from baseline to the end of Week 6 in ISI total score by baseline ISI score ( $\geq$ 15 versus <15, using the randomization stratification factor as entered into IWRS)

The change in ISI score from baseline to the end of Week 6 will be analyzed using an ANCOVA model. The ANCOVA model will include factors for treatment and region, and baseline ISI score as a continuous covariate. A 90% CI for the difference in LSMeans and p-value will be calculated based on the contrast test statistic for each JNJ-42847922 dose level.

The cumulative response rate, defined as the percentage of subjects experiencing at least a given value of percent reduction from baseline to the end of Week 6 in ISI score, will be presented graphically, using observed data.

## 5.3.4. Change in Hamilton Anxiety Rating Scale (HAM-A)

## 5.3.4.1. Definition

A secondary efficacy endpoint is the change from baseline to the end of Week 6 in the HAM-A total score. The original 14-item clinician-administered HAM-A scale assesses the severity of different anxiety-related symptoms. It is a commonly used, validated scale in clinical trials assessing anxiety. However, the original HAM-A lacks instructions for administration and clear anchor points for the assignment of severity ratings. For this reason, the structured interview guide version (SIGH-A) will be used in this study.

Each of the 14-items in the scale is scored on a 5-point scale, ranging from 0 (not present) to 4 (very severe, symptom is incapacitating). A total score (0 to 56) is calculated by adding the scores of all 14 items, where 0-13 indicates normal range, 14-17 indicates mild severity, 18–24 mild to moderate severity, 25–30 moderate to severe, and  $\geq$ 31 severe. Higher scores represent a more severe condition.

The HAM-A change from baseline at Week 6 is calculated as (HAM-A total score at Week 6 – Baseline HAM-A total score). Negative changes in HAM-A total score indicate improvement.

The somatic factor score of HAM-A is defined as the sum of items 7 to 13; and the psychic factor score of HAM-A is defined as the sum of items 1-6 and 14.

#### 5.3.4.2. Analysis Methods

Descriptive statistics of the actual values on Baseline, Day 8, Day 22, and Day 42 and the change from baseline to Day 8, 22, and 42 will be presented for HAM-A total score, and HAM-A somatic and psychic factor scores by treatment group.

The change from baseline to Day 8, 22, and 42 in HAM-A total score will be analyzed using the same MMRM as described in Section 5.2.3.1 for the primary efficacy endpoint, with the continuous covariate "baseline MADRS total score" changed to "baseline HAM-A total score".

As a sensitivity analysis, the change in HAM-A total score from baseline to the end of Week 6 will be analyzed using an ANCOVA model, using LOCF data. The derivation of the LOCF values is described in Section 5.2.3.3. The ANCOVA model will include factors for treatment, region, baseline insomnia status (present/absent), and baseline HAM-A total score as a continuous covariate. A 90% CI for the difference in LSMeans and p-value will be calculated based on the contrast test statistic for each JNJ-42847922 dose level.

In addition, a frequency distribution over time of the HAM-A total score categories and HAM-A individual item scores at each time point will be provided by treatment group.

The shift in HAM-A total score category from baseline to each time point will be presented by treatment group.

The correlations between HAM-A total score and MADRS total score will be evaluated using Pearson and Spearman correlation coefficients. These correlations will look at the correlations of the actual values at each time point, as well as the change from baseline. Scatter plots will also be presented.

## 5.3.5. Response of Anxiety Symptoms

#### 5.3.5.1. Definition

A secondary efficacy endpoint is the proportion of responders on anxiety symptoms scale at the end of Week 6, defined as a  $\geq$ 50% improvement in the HAM-A total score from baseline to the end of Week 6. The calculation of the HAM-A total score is described in Section 5.3.4.1. The percentage change from baseline for HAM-A total score is calculated as 100\*(HAM-A total score at Day X – Baseline HAM-A total score)/(Baseline HAM-A total score). Negative percent changes in HAM-A total score indicate improvement (eg, percent change < -50% indicates improvement >50%).

A subject is defined a responder (yes=1) at a given time point if the percent reduction in HAM-A is  $\geq$ 50%. Subjects who do not meet such criterion will be considered as non-responders and will be assigned a value of 0 (i.e., no). Observed case analysis, i.e., no imputation for subjects with missing values, will be explored.

## 5.3.5.2. Analysis Methods

The number and percentage of subjects who achieve a response will be summarized at each time point during the double-blind phase by treatment group.

The cumulative response rate, defined as the percentage of subjects experiencing at least a given value of percent reduction from baseline to the end of Week 6 in HAM-A total score, will be presented graphically, for both observed and LOCF data.

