2. OBJECTIVES, ENDPOINTS, AND HYPOTHESIS

2.1. Objectives and Endpoints

Objectives	Endpoints	
Primary		
• To assess the dose-response relationship of up to 3 doses of JNJ-42847922 (20, and 40 mg, with 10 mg potentially added at the interim analysis) compared to placebo as adjunctive therapy to an antidepressant drug in improving depressive symptoms in subjects with MDD who have had an inadequate response to current antidepressant therapy with a selective serotonin reuptake inhibitor (SSRI) or serotonin-norepinephrine reuptake inhibitor (SNRI).	Change from baseline to the end of Week 6 in the MADRS total score.	
To assess the safety and tolerability of JNJ-42847922 compared to placebo as adjunctive therapy to an antidepressant in subjects with MDD.	• Safety assessments, including adverse events, laboratory values, ECG, vital signs, physical exam, the C-SSRS, the Arizona Sexual Experiences Scale (ASEX), and the Physician Withdrawal Checklist (PWC).	

Objectives	Endpoints	
To assess the efficacy of JNJ-42847922 compared to placebo as adjunctive therapy to an antidepressant in improving depressive symptoms in subjects with MDD with significant insomnia symptoms (baseline Insomnia Severity Index [ISI] score ≥15) versus those without significant insomnia symptoms (baseline ISI score <15).	 Correlation between baseline ISI score as a continuous variable and change from baseline to the end of Week 6 in the MADRS total score. Change from baseline to the end of Week 6 in the MADRS total score in subjects with baseline ISI score ≥15 versus subjects with baseline ISI score <15. Shift in ISI score category from baseline to the end of Week 6. 	
To assess the efficacy of JNJ-42847922 compared to placebo as adjunctive therapy to an antidepressant in improving: Response and remission of depressive symptoms	 Proportion of responders on depressive symptoms scale, defined as a ≥50% improvement in MADRS total score from baseline to the end of Week 6. Proportion of subjects with remission of depressive symptoms, defined as a MADRS total score ≤8, ≤10, or ≤12 at the end of Week 6. 	
- Anxiety symptoms	 Change from baseline to the end of Week 6 on the 14-item Hamilton Anxiety Rating scale (HAM-A) total score. 	
Response of anxiety symptoms	 Proportion of responders on anxiety symptoms scale, defined as a ≥50% improvement in the HAM-A total score from baseline to the end of Week 6. 	

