11.3. Efficacy Analyses

Primary estimand

The primary estimand, the main clinical quantity of interest to be estimated in the study, is defined by the following 3 components:

Population: subjects with MDD who have had an inadequate response to current antidepressant therapy with an SSRI/SNRI.

Endpoint: change in MADRS total score from baseline to the end of Week 6.

Measure of Intervention: the effect of the initially randomized treatment together with the oral SSRI/SNRI antidepressant that would have been observed had all subjects remained on their treatment throughout the double-blind phase.

The primary analysis will be based on the FAS and the MADRS total scores collected during the double-blind phase.

The primary efficacy endpoint will be evaluated at a 1-sided significance level of 0.05 using the MCP-Mod approach to test for dose-response. For all other analyses of the primary efficacy endpoint and for all other efficacy endpoints, no multiplicity adjustment will be done and nominal 1-sided p-values will be presented.

Primary efficacy endpoint

The primary efficacy endpoint is the change in MADRS total score from baseline to the end of Week 6. A mixed model for repeated measures (MMRM) analysis of the observed data from the placebo and JNJ-42847922 groups will be used as the method of addressing missing data. The MMRM will include region, time, treatment (placebo and JNJ-42847922 dose groups), baseline insomnia status (present/absent), and treatment-by-time interaction as factors and baseline MADRS total score as a covariate. An unstructured variance-covariance matrix will be used. Subjects in the FAS who do not have complete data will still contribute to the estimates at the end of Week 6, but will have less weight in the analysis than those subjects with complete data. The final analysis will use the generalized MCP-Mod approach⁴⁵ (a hybrid methodology that combines multiple comparison procedures with modeling techniques), which will be applied towards estimates obtained from the MMRM analysis to establish a dose-response signal and to

determine dose(s) to be used in the Phase 3 studies. MCP-Mod has been qualified by the European Medicines Agency. ¹⁰

In conjunction, the comparison between JNJ-42847922 and placebo will also be performed using the appropriate contrasts directly from the MMRM analysis using estimates at the end of Week 6.

Secondary efficacy endpoints

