## 5. EFFICACY

All efficacy analyses will be based on the full analysis set.

The efficacy variables for this study are listed in Table 4.

Efficacy Variable		Endpoint
MADRS	• Change from baseline to the end of Week 6 in the MADRS total score	Primary
	• Correlation between baseline ISI score as a continuous variable and change from baseline to the end of Week 6 in the MADRS total score.	Secondary
	• Change from baseline to the end of Week 6 in the MADRS total score in subjects with baseline ISI score $\geq$ 15 versus subjects with baseline ISI score	Secondary

 Table 4: Efficacy Variables

Efficacy Variable		Endpoint
	<15.	
	
 
Proportion of responders on depressive symptoms scale (≥50% improvement in the MADRS total score from baseline to the end of Week 6)
 
	Secondary
	
 
Proportion of subjects with remission on depressive symptoms scale (MADRS total score ≤8, ≤10, ≤12 at the end of Week 6)
 
	Secondary
	• Change from baseline to the end of Week 6 in the MADRS total score in subjects with MDD with anxious distress versus subjects with MDD without anxious distress.	Secondary
	• Change from baseline to the end of Week 6 in the MADRS-6 total score	Secondary
ISI	• Shift in ISI score category from baseline to the end of Week 6.	Secondary
HAM-A	• Change from baseline to the end of Week 6 in the HAM-A total score	Secondary
	
 
Proportion of responders on anxiety symptoms scale (≥50% improvement in the HAM-A total score from baseline to the end of Week 6)
 
	Secondary
CGI-S	• Change from baseline to the end of Week 6	Secondary
SDS	• Change from baseline to the end of Week 6	Secondary
PHQ-9	• Change from baseline to the end of Week 6	Secondary
SHAPS	• Change from baseline to the end of Week 6	Secondary
PROMIS-SD	• Change from baseline to the end of Week 6	Secondary
PROMIS-Fatigue	• Change from baseline to the end of Week 6	Secondary
PGI-S	• Change from baseline to the end of Week 6	Secondary
EQ-5D-5L, VAS and health status index	• Change from baseline to the end of Week 6	Secondary
WLQ	• Change from baseline to the end of Week 6	Secondary

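### HAM-A response is a secondary endpoint with a versus-placebo objective, but SAP 5.3.5.2 plans only per-arm summaries, with no between-arm estimate or interval

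*SAP*

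**What the plan says.** Protocol 2.1 sets the objective: "To assess the efficacy of JNJ-42847922 compared to placebo as adjunctive therapy to an antidepressant in improving" a list of outcomes, one of which is response of anxiety symptoms. The matching endpoint, assessed at Week 6 against baseline, is "Proportion of responders on anxiety symptoms scale, defined as a ≥50% improvement in the HAM-A total score". SAP Table 4 lists it as secondary ("Proportion of responders on anxiety symptoms scale"), and SAP 5.3.5.1 repeats that status: "A secondary efficacy endpoint is the proportion of responders on anxiety symptoms scale at the end of Week 6".

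The analysis in SAP 5.3.5.2 has two parts. The first is "The number and percentage of subjects who achieve a response will be summarized at each time point during the double-blind phase by treatment group". The second is a graph of the cumulative response rate, on observed and LOCF data. SAP 5.1.2 and 5.3.5.1 add the missing-data handling: missing values count as non-response, with an observed-case version alongside.

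For MADRS response, SAP 5.3.1.3 goes further and adjusts for both stratification factors: "The point estimate and 2-sided 90% confidence interval will be provided for the relative response using a Mantel-Haenszel test". For MADRS remission, SAP 5.3.2.2 gives a point estimate and 90% interval for the "relative risk of remission using a Mantel-Haenszel test controlling for region and baseline insomnia status".

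Protocol 11.3 states that "for all other efficacy endpoints, no multiplicity adjustment will be done and nominal 1-sided p-values will be presented". The same section, under secondary endpoints, names only frequency distributions for the numbers of responders and remitters.

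**The concern.** The objective asks how the drug compares with placebo on anxiety response, and the planned output describes each arm separately. A reader of the study report would have one percentage per arm and would have to judge the difference unaided. The report would give no interval and no adjustment for the randomization strata.

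Protocol 1.2 says the results will be used to select doses and endpoints for Phase 3, so the precision of a candidate endpoint is of practical interest. If a comparison is wanted later, its method would have to be chosen after the data are known. The SAP gives no reason for treating this binary endpoint differently from the two MADRS ones.

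**Working it through.** **Step 1. Set the binary secondary endpoints in SAP Table 4 side by side.**

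| Endpoint | SAP section | Per-arm n and % | Between-arm estimate with 90% CI |
|---|---|---|---|
| MADRS response | 5.3.1.3 | yes | relative response, Mantel-Haenszel, region and insomnia status |
| MADRS remission | 5.3.2.2 | yes | relative risk, Mantel-Haenszel, region and insomnia status |
| HAM-A response | 5.3.5.2 | yes | none |

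PHQ-9 response and remission (SAP 5.3.8.2) are also summarized by arm only, but Table 4 lists PHQ-9 as a change score, so they are not endpoints in their own right.

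**Step 2. Look for a comparison elsewhere.** SAP 5.1.2 gives only the missing-data rule. SAP 5.3.4.2 compares arms on HAM-A total score and does not mention response. The SAP 5.1.1 sentence that parallels the protocol's p-value statement is incomplete in the available text, so nothing here rests on it.

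**Step 3. Plan's own figures.** The documents give no HAM-A response rate and no power for this endpoint. The only sizing figure for the final analysis is about 85% average power for the MCP-Mod test on MADRS change. With the SAP candidate models, a difference of 4.5, SD 10, 1-sided 0.05 and 280 × 0.75 = 210 completers, that recomputes to 86.2% without a 10 mg arm (85.2% if 10 mg is added at an assumed 2:1:1:1). It is not in dispute.

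**Step 4. Illustrate the missing interval.** Assumptions: response 30% on placebo and 45% on one dose, and 2:1:1 allocation throughout. Then 280 subjects give 140 placebo and 70 per dose with missing counted as non-response. For observed cases, 25% dropout gives 105 and 52. Strata are ignored.

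- Risk difference: SE = √(p₀q₀/n₀ + p₁q₁/n₁).
  - 140/70: √(0.21/140 + 0.2475/70) = 0.0710. The 90% half-width is 1.645 × 0.0710 = 0.117, so 15 points runs from 3 to 27.
  - 105/52: √(0.21/105 + 0.2475/52) = 0.0822. The half-width is 0.135, so 1 to 29 points.
- Relative response: 0.45/0.30 = 1.50, with SE of the log = √(q₀/(p₀n₀) + q₁/(p₁n₁)).
  - 140/70: √(0.70/42 + 0.55/31.5) = 0.185. The 90% CI is 1.50 × exp(±0.304), or 1.11 to 2.03.
  - 105/52: √(0.70/31.5 + 0.55/23.4) = 0.214. The 90% CI is 1.50 × exp(±0.352), or 1.06 to 2.13.
- Power at 1-sided 0.05 = Φ(0.15/SE − 1.645): 68% for 140/70 and 57% for 105/52. With placebo rates from 25% to 40% and the same 15-point difference, the ranges are 66% to 70% and 56% to 59%.

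**Step 5. Vary the allocation.** Suppose 10 mg is added after 160 subjects and the remaining 120 are split 2:1:1:1 (an assumption). Placebo would have 80 + 48 = 128 and 10 mg would have 24. At the same rates, SE = √(0.21/128 + 0.2475/24) = 0.109 and the half-width is about 18 points. The interval therefore depends heavily on an allocation that is not yet fixed.

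**The case against.** The strongest reply is that the SAP does what the protocol asks for this type of endpoint. Protocol 11.3 names frequency distributions for responders and remitters and leaves the remaining secondary analyses to the SAP. On that reading the p-value sentence mainly says that no multiplicity adjustment is made. This stands in part: the SAP matches one sentence of 11.3 and falls short of another, so there is no flat contradiction. It does not explain the difference in treatment, because the same frequency sentence covers MADRS responders and remitters and the SAP still gives both a between-arm estimate.

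Nor does the p-value statement by itself separate HAM-A response from its comparators. SAP 5.3.1.3 and 5.3.2.2 name an estimate and an interval but no explicit p-value for the Week 6 proportions. The clear difference is the missing estimate and interval.

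It can also be said that little is lost. HAM-A total score is compared by MMRM, and by LOCF ANCOVA with a 90% interval and p-value for each dose (SAP 5.3.4.2). The trial is not confirmatory, and a reader can compute a crude interval from the counts. All of that is true and lowers the severity. A mean difference still does not estimate a responder contrast, and a crude interval is neither stratified nor prespecified.

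**Conclusion.** The point holds and is minor. A listed secondary endpoint with a comparative objective has no comparative analysis, while its two binary counterparts in Table 4 do.

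A reader might infer more than the documents support:

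- **That anxiety goes uncompared with placebo.** It does not; the gap concerns the responder endpoint only.
- **That this is the one secondary endpoint left descriptive.** It is not. EQ-5D-5L (SAP 5.3.13.2) and WLQ (SAP 5.3.14.2) are also descriptive, although protocol 11.3 assigns the primary MMRM to any secondary endpoint defined as a change from baseline.
- **That nothing could be said about the difference.** The counts allow a crude comparison. What is missing is a prespecified, stratified one.

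The primary analysis is unaffected. The interval and power figures only illustrate the precision such a comparison might have. They assume both the response rates and, except in the last step, 2:1:1 allocation throughout.

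**What to change.** Add to SAP 5.3.5.2: *For each JNJ-42847922 dose versus placebo at the end of Week 6, the relative response on HAM-A with a 2-sided 90% CI and a nominal 1-sided p-value will be obtained by the Mantel-Haenszel method, controlling for region and baseline insomnia status. Missing values will be counted as non-response, and the analysis will be repeated on observed cases.*

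The estimate and interval match what is planned for MADRS response. The p-value follows the general statement in protocol 11.3 and goes one step beyond what the SAP names for the MADRS proportions. A risk difference is not needed for parity.

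The alternative is to state in the SAP that HAM-A response is descriptive and to narrow the p-value sentence in protocol 11.3 accordingly.

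The first option costs a short addition to the SAP and an adapted run of a method already planned. Its downside is one more unadjusted nominal comparison, in a set that the protocol already leaves uncontrolled for Type I error.
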